4.6 Clinical Laboratory Tests

- Clinical laboratory results beyond the detectable limits will be reported as detectable limits for calculating descriptive statistics.
- All the laboratory test results will be included in the data listings as reported.

4.7 Handling of Partial Dates for Medications

When determining prior or concomitant medications, partial start dates of prior and concomitant medications will be assumed to be the earliest possible date consistent with the partial date.

For the purposes of analysis, incomplete medication starts and stop dates will be imputed.

- If a medication start date is incomplete, January will be imputed for missing month and/or the first day of the month will be imputed for missing day.
- If a medication stop date is incomplete, December will be imputed for missing month and the last day of the month will be imputed for missing day.
- If the imputed medication stop date is after the date of study completion, the date of study completion will be used instead.

4.8 Handling Partial Date for Adverse Events

When determining treatment emergent AEs, partial dates will be handled as follows.

- If the day of the month is missing, the onset day will be set to the first day of the month unless it is the same month and year as first dose date. In this case, the onset date will be assumed to be the first date of treatment.
- If the onset day and month are both missing, the day and month will be assumed to be January 1, unless the event occurred in the same year as the study treatment start. In this case, the event onset will be coded to the day of treatment start to conservatively report the event as treatment-emergent.
- A missing onset date will be coded as the day of treatment start. If the resulting onset date is after a reported date of resolution, the onset date will be set equal to the date of resolution.
- Imputation of partial dates is used only to determine whether an event is treatmentemergent; data listings will present the partial date as recorded in the eCRF.

4.9 Handling Partial Date for Date of Diagnosis & Platelet Transfusion Date

• If a date of diagnosis is incomplete, July will be imputed for missing month and the 15th day of the month will be imputed for missing day.

5. PLANNED ANALYSIS

5.1 Changes from Planned Analyses in the Protocol

An exploratory efficacy endpoint was included which was not detailed in the protocol: Month 3 durable platelet response defined as the proportion of subjects achieving at least 3 out of 4 weekly platelet counts $\geq 50 \times 10^9$ /L during the last 4 weeks of the 12 week Treatment Period in the Core Phase in the absence of rescue medication.

Bleeding Adverse Events of Special Interest identified using a MedDRA SMQ were further defined as clinically significant blood loss using reported CTCAE grades instead of WHO bleeding grades, as WHO bleeding grades collected at study visits are not linked to individual adverse events.

5.2 Interim Analysis

No formal interim analysis is planned for this study. An IDMC will be convened for this study, primarily to monitor safety at regular intervals. An IDMC charter, detailing all aspects of the IDMC's scope of review and procedures, will be described in a separate document. In addition, ongoing safety data will be reviewed by the Sponsor in a blinded fashion for each age cohort. Interim PK/PD data will be analyzed by an unblinded designee.

5.3 Final Analyses and Reporting

This study consists of a double-blind, placebo-controlled period (Core Phase) and an open-label extension period (Extension Phase). The database will be locked, and the treatment assignment will be unblinded, when the last subject completes the Core Phase of the study. All data from the Core Phase and Open Label Extension Phase available in the locked database will be included in the statistical analyses. When the last subject completes the Extension Phase, additional extension data will be summarized and included in an updated Clinical Study Report.

6. ANALYSIS POPULATION

6.1 Screened Set

Screened Set includes all subjects with a signed informed consent form.

6.2 Core Phase Full Analysis Set (FAS)

The Core Phase Full Analysis Set (FAS) will include all randomized subjects.

Core Phase FAS is used for efficacy analysis in Core Phase. The analysis will be performed based on the randomized study drug.

6.3 Extension Phase Full Analysis Set (FAS)

The Extension Phase Full Analysis Set (FAS) will include all randomized subjects who entered Open Label Extension.

Extension Phase FAS is used for efficacy analysis in Extension Phase. The analysis will be performed based on the open label study drug.

6.4 Core Phase Safety Analysis Set

The Core Phase Safety Analysis Set includes all subjects who receive at least one dose of study drug.

The analysis will be performed based on the actual study drug received.

6.5 Extension Phase Safety Analysis Set

The Extension Phase Safety Analysis Set includes all subjects who receive at least one dose of study drug during Open Label Extension Phase.

The analysis will be performed based on the actual study drug received.

6.6 Per-Protocol Analysis Set (PPS)

The per-Protocol Analysis Set (PPS) will include a subset of subjects from the FAS who do not meet any criteria that would potentially impact the evaluation of the efficacy endpoints. A full list of the specific criteria will be finalized in a separate document prior to database lock and unblinding. Examples of these criteria may include:

- Use of certain prohibited concomitant medications
- Selected Inclusion/Exclusion criteria not met for the Core phase
- Lack of compliance with study medication during the Core phase
- Study Discontinuation resulting in an inability to assess the primary efficacy endpoint
- Assigned to incorrect treatment (mis-randomization) or receiving incorrect study medication

The analysis will be based on the actual study drug received.

6.7 Application of Analysis Set

The analysis sets that will be used for creating the summary tables of each type are provided in Table 1 (Core Phase) and Table 12 (Extension Phase).

Table 1. Application of Populations to Tables in Core Phase

Туре	Safety	FAS	PPS
Disposition		X	
Demographics and baseline characteristics		X	
Protocol deviations		X	
Medical history and disease history		X	
Prior/concomitant medications/procedure		X	
Safety evaluations	X		

Туре	Safety	FAS	PPS
Primary efficacy evaluations		X	X
Secondary efficacy evaluations		X	X

Table 2. Application of Populations to Tables in Extension Phase

Туре	Safety	FAS
Disposition	X	
Demographics and baseline characteristics	X	
Protocol deviations	X	
Medical history and disease history	X	
Prior/concomitant medications/procedure	X	
Safety evaluations	X	
Primary efficacy evaluations		X
Secondary efficacy evaluations		X

7. STATISTICAL CONSIDERATIONS

All analyses described in this plan are considered a priori analyses in that they have been defined prior to locking the database. All other analyses, if any, designed subsequently to locking the database will be considered post hoc analyses and will be described as exploratory analyses in the Clinical Study Report.

All summaries and statistical analysis will be performed using SAS v9.4 or later.

7.1 General Statistical Procedures

Categorical variables will be summarized with number and percentage of subjects with a response in the category. Percentages will be based on number of subjects in the given population as noted. Number of subjects with missing information will also be included. Percentages will be reported to one decimal place.

A 2-sided 95% exact binomial (Clopper-Pearson) confidence interval (CI) for categorical variables without multiplicity adjustment will be provided where appropriate for efficacy analysis.

Continuous variables will be summarized with number of subjects (n), mean, standard deviation (SD), median, minimum (min) and maximum (max). Mean and median will be reported to 1 more decimal place than the raw data, while the SD will be reported to 2 more decimal places than the raw data. Minimum and maximum will be reported with the same number of decimals as the original data.

Unless otherwise stated, statistical summaries will be performed for each study phase (Core Phase and Extension Phase). Core Phase analysis will be performed by treatment for each cohort and overall. Open Label Extension Phase analysis will be performed by cohort and overall.

Data that is not summarized will be listed only. Unless otherwise specified in the text, all listings will be provided for the Full Analysis Set and will be ordered by subject number, study phase (Core Phase and Extension Phase) and visit and repeated by cohort for available data.

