3.6 Exploratory Endpoints

- Platelet count assessments and platelet response during the Extension Phase.
- Subject reported palatability and parent/caregiver reported acceptability assessed by a palatability/acceptability questionnaire administered after the first dose of the powder for oral suspension.

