6.3.2 Early Termination

A subject may be early terminated from the Core Phase or the Extension Phase for any of the following reasons:

- A platelet count $>250\times10^9$ /L after 2 weeks of once weekly dosing for any age cohort.
- Subject or the subject's LAR, as applicable, wishes to withdraw consent/assent for any reason.
- Subject non-compliance or unwillingness to comply with the procedures required by the protocol.
- Occurrence of any medical condition that exposes the subject to substantial risk and/or does not allow the subject to adhere to the requirements of the protocol.
- Any SAE, clinically significant AE, severe laboratory abnormality, intercurrent illness, or other medical condition which indicates to the Investigator that continued participation in the study is not in the best interest of the subject.
- Pregnancy.
- Requirement of a prohibited concomitant medication (Section 8).
- Investigator discretion.
- Sponsor request.
- Termination of the study by the Sponsor or a regulatory agency.

In addition, a subject may be early terminated from the Extension Phase if they have a platelet count $<30\times10^9/L$ after 3 weeks of once daily dosing at the cohort defined maximum dose.

Every effort should be made during the conduct of the study to limit the extent of missing data. Except for subjects who are being withdrawn from the Core Phase due to a lack of treatment effect (Section 5.3), subjects who prematurely discontinue the study drug should remain in the study for collection of data, unless the subject withdraws consent. If a subject is early terminated from the Core Phase of the study after the first dose of study drug, but prior to the end of the PK blood collection (Visit 12/Week 10), consideration should be given to collecting all remaining PK blood draws, if possible.

If a subject is early terminated from the study after randomization, the Early Termination procedures (Section 9.3) should be performed. Subjects withdrawn from the study after randomization will not be replaced, regardless of the reason for withdrawal.

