7 STUDY TREATMENTS

7.1 Treatment Groups

The 12 week Core Phase of this Phase 3b study is randomized, double-blind, and placebo-controlled. At Day 1/Visit 2, subjects will be randomized in a 3:1 ratio to receive either avatrombopag or matching placebo.

The Extension Phase of this study is open-label therefore all subjects will receive avatrombopag.

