To control the family-wise Type I error rate at a significance level of $\alpha = 0.05$ (2-sided), a step-down closed testing procedure will be used when testing the secondary efficacy endpoints. Starting with the key secondary efficacy endpoint, if the test is significant at $\alpha = 0.05$, then the test on the next endpoint will be considered inferential; otherwise, the tests on the subsequent endpoints will be considered descriptive only. This process will be repeated from the top of the hierarchy for the remaining endpoints.

The efficacy variables collected during the Open Label Extension Phase will be summarized descriptively.

For the Core Phase, observed values and change from baseline over time for platelet counts will be summarized. For the Core Phase, WHO bleeding scale will be summarized by visit.

For the Extension phase, observed values for platelet counts and WHO bleeding scale will be summarized by visit.

Blood product transfusions will be summarized for both the Core Phase and the Open Label Extension Phase including the following variables:

- Number and percentage of subjects with at least one blood product transfusion
- Total number of blood product transfusions
- Type of blood product
- Reasons for transfusion
- Number of packs/units per transfusion

Platelet count and blood transfusions will be listed for the Full Analysis Set.

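### Extension results are not split by former Core arm, so first response in children coming off placebo is mixed with maintained response in children already on avatrombopag

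*SAP*

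**What the plan says.** SAP 7.1 sets different grouping rules for the two phases. For the Core, "Core Phase analysis will be performed by treatment for each cohort and overall". For the Extension, "Open Label Extension Phase analysis will be performed by cohort and overall". No later SAP section restores a split by randomized arm.

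SAP 6.3 defines the efficacy set: "The Extension Phase Full Analysis Set (FAS) will include all randomized subjects who entered Open Label Extension". It adds: "The analysis will be performed based on the open label study drug". Protocol 7.1 says "The Extension Phase of this study is open-label therefore all subjects will receive avatrombopag", so this makes one treatment group. SAP 4.4 counts study days from the first dose within each phase, so the clock returns to Day 1 for both former arms.

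For outcomes, SAP 7.4 says "For the Extension phase, observed values for platelet counts and WHO bleeding scale will be summarized by visit". Protocol 3.6 lists as exploratory "Platelet count assessments and platelet response during the Extension Phase", but SAP 7.4 gives Extension response no definition, denominator or failure rule of its own.

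On leaving the phase, Protocol 6.3.2 says "a subject may be early terminated from the Extension Phase if they have a platelet count" below 30×10^9/L after 3 weeks of once-daily dosing at the cohort's maximum dose. The same section also allows early termination for a count above 250×10^9/L after 2 weeks of once-weekly dosing.

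**The concern.** At Visit E-1 the two former arms are at different points. One starts avatrombopag; the other has taken it for up to 12 weeks. A reader of the 2-year platelet course wants to know how quickly children respond and whether response lasts. A single pooled column answers neither question cleanly: a rise over the first months could be onset in the former-placebo children, further gain in the continuing children, or both. A flat course could hide onset in one group and loss in the other.

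Safety has the same problem. SAP 7.5.2 assigns to the Extension every treatment-emergent event that starts on or after the first Extension dose. Early reactions in newly exposed children are then counted together with events in a continuing group up to three times as large.

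A second, separate mechanism acts on the platelet summaries. Means and medians of observed values use only children with a count at that visit, and one permitted reason for leaving is a persistently low count.

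**Working it through.** **The plan's own figures.** The documents give no number for the Extension course. The nearest figures are the planning assumptions in SAP 2.2: 54 and 18 children, durable response 41.3% and 3.4%, and at least 90% power with Fisher's exact test at two-sided 0.05. Exact enumeration over both binomials gives 94.5%, so that statement reproduces. The same rates are used below as stand-ins.

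**Time on drug at one nominal visit.** Protocol Table 8 puts E-2 at Day 30. A former-placebo child then has about 30 days of avatrombopag. A child who completed the Core on avatrombopag has about 84 + 30 = 114 days, nearly four months. A child who left the Core early for lack of effect falls in between.

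**Effect of pooling.** Assume all 72 enter and the durable-response rates stand in for the share with a count of at least 50×10^9/L at a visit.

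- At E-1: (54 × 0.413 + 18 × 0.034) / 72 = (22.302 + 0.612) / 72 = 31.8%.
- Once the former-placebo children reach 41.3% and nobody else changes: 41.3%.
- Rise: 18/72 × (41.3 − 3.4) = 9.5 points, all of it in the former-placebo children.
- If the on-drug rate were 60% or 80%, the pooled figure would go from 45.9% to 60%, or from 60.9% to 80%.
- Split by Core arm, the first case reads 41.3% throughout in one column and 3.4% rising to 41.3% in the other.

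**Direction of selective exit.** Take fixed counts that never change, assumed to be 90 for responders and 20 for non-responders (×10^9/L), with 41.3% responders.

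- Everyone present: 0.413 × 90 + 0.587 × 20 = 48.9.
- Half of the non-responders gone: (0.413 × 90 + 0.2935 × 20) / (0.413 + 0.2935) = 60.9.
- No loss, or loss unrelated to response: no change.

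This shows direction only. The two counts and the exit fraction are assumptions, and treating every durable non-responder as eligible to leave exaggerates the size.

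**Data cut.** Under SAP 5.3 the first report uses whatever Extension data exist at the Core lock. Cohorts open in descending age order, so later visits in the overall column will hold mainly earlier, older entrants. A by-visit denominator therefore has to be the children due for that visit.

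**The case against.** The best defence is that little depends on this output. Extension response is exploratory, SAP 7.4 makes Extension efficacy descriptive, and no Extension efficacy test is planned. Summaries of continuous values carry n, so shrinkage would show. Disposition with reasons for discontinuation is planned for the Extension, and platelet counts and adverse events are listed by child. First-exposure adverse events are already tabulated against placebo in the planned 54 Core avatrombopag children. The former-placebo group is small: 7, 7 and 4 by cohort at most.

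All of that is fair, and it limits the importance of the point. It does not supply the missing split. Disposition follows the same SAP 7.1 grouping, so its Extension columns are pooled too, and it gives totals and reasons rather than exits by visit. Listings leave the reader to rebuild the table.

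On missing data the defence also has some force. SAP 7.1 bases categorical percentages on the number in the given population and shows the number missing. SAP 7.4 counts children without enough data to determine response as non-responders; that sentence has no phase limit, although the text around it concerns the Core. For WHO grade, or for an Extension response rate, the denominator is therefore unclear rather than plainly limited to children still present. Protocol 6.3.2 also asks children who stop study drug early to stay for data collection, so some may still contribute counts.

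**Conclusion.** The grouping rule is a real weakness, and it is cheap to repair. As written, the Extension course cannot separate onset from maintenance, and Extension adverse events cannot be divided into first and continued exposure. The 9.5-point illustration assumes that all 72 enter, although entry is optional and conditional, and that durable-response rates stand in for by-visit response.

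A reader might infer more: that the planned course will show an improvement no child had. The documents do not support that. Pooling cannot create such a rise, because the former-placebo children in the illustration really improve. Only selective exit could, and no Extension dropout rate is given. It would also be tempting to apply exit fractions to the 58.7% without durable response (100 − 41.3) and report a large inflation of the response rate. That would assume a denominator the SAP does not specify. It would also treat every child who misses 6 of 8 weekly counts as eligible for an exit that needs a count below 30×10^9/L after 3 weeks at maximum dose and is optional even then. The exit above 250×10^9/L removes high counts and pulls the other way. Selective exit can therefore flatter later visits, by an unknown amount. No primary or secondary result is touched.

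**What to change.** In SAP 7.1 and 7.4:

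1. Present Extension platelet, WHO bleeding, exposure and treatment-emergent adverse event summaries by randomized Core arm (placebo to avatrombopag; avatrombopag to avatrombopag) and in total.
2. Add one platelet summary by time since first avatrombopag dose.
3. Beside the observed values at each visit, show the number of Extension FAS children due for that visit by the data cut, the number who have left with the reason, and the proportion of those due with a count of at least 50×10^9/L. Count exits for lack of effect as non-responders, and state how all other exits are counted, including those for high counts, adverse events and withdrawn consent.

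The cost is SAP wording and a few more tables or columns from data already collected. The Core blind is broken at the Core lock, so the split reveals nothing early. The former-placebo column will be small and is best shown overall rather than within each age cohort. No design, dosing or clinical rule changes.

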7.2 Subject Enrollment and Disposition

7.2.1 Subject Enrollment

The number of subjects screened, number of screen failure subjects and number of subjects in each analysis set will be provided.

Listing will be provided for Screened Set.

7.2.2 Subject Disposition

Subject disposition will be summarized (based on Section 7.1) for each phase including:

- Number and percentage of subjects who completed the study phase (Core/Extension)
- Number and percentage of subjects still on treatment (Core/Extension)
- Number and percentage of subjects who discontinued from the study phase (Core/Extension) and reasons for study discontinuation
- Number and percentage of subjects who discontinued the study drug and reasons for study drug discontinuation

Subject disposition will be listed for the Full Analysis Set. A separate listing will be provided for screen failure subjects with reasons for screen failure.

7.2.3 Protocol Deviations

Protocol deviations will be reviewed, assessed and documented by sponsor personnel before database lock.

The number and percentage of subjects with a major protocol deviation will be tabulated by category for the Full Analysis Set for each phase. Details of the major protocol deviations will be provided in a listing.

The number and percentage of subjects who are excluded from the PPS will be summarized by treatment group, along with reasons for exclusion. Subjects excluded from PPS will also be presented in a data listing.

7.3 Demographic and Baseline Disease Characteristics

7.3.1 Demographic and Baseline Characteristics

Demographic and baseline characteristics will be summarized (based on Section 7.1) including:

- Age (years) at randomization
- Sex
- Ethnicity
- Race
- Region (US, Europe)
- Weight (kg)
- Height (cm)
- BMI (kg/m²)

Demographics and baseline characteristics will be listed for the Full Analysis Set.

7.3.2 ITP History

ITP history will be summarized (based on Section 7.1) including the following information:

- Time from primary ITP diagnosis to first dose date (weeks), calculated as (first dose date
 date of diagnosis of primary ITP+1)/7
- Number and percentage of subjects with splenectomy
- Number and percentage of subjects who received a previous platelet transfusion
- Time from last platelet transfusion to first dose date (weeks) defined as (first dose date last platelet transfusion date + 1)/7
- Number and percentage of subjects who received different types of ITP medications since diagnosis
- Number and percentage of subjects treated with a TPO agonist
- Number and percentage of subjects by type of treatment received (Eltrombopag, Romiplostim, rhTPO and Other)
- Number and percentage of subjects who responded to any prior TPO agonist treatment

ITP history will be listed for the Full Analysis Set.

